4.6.3 Irinotecan: IV over 90 minutes

During 'Upfront' Window Therapy for All High-Risk Patients

50 mg/m^2/dose (1.67 mg/kg/dose for patients  $< 10$  kg) [Maximum dose: 100 mg] on Days 1-5 of Cycles 1 and 2.

During Post 'Upfront' Window Therapy for All High-Risk Responder Patients

50 mg/m^2/dose (1.67 mg/kg/dose for patients  $< 10$  kg) [Maximum dose: 100 mg] on Days 1-5 of Cycles 7 and 10.

See: [https://members.childrensoncologygroup.org/prot/reference\\_materials.asp](https://members.childrensoncologygroup.org/prot/reference_materials.asp)

Under Standard Sections for Protocols – Supportive Care Guidelines for prophylactic antibiotics and treatment recommendation for diarrhea secondary to irinotecan.

#### 4.6.4 Temsirolimus: IV over 30 minutes

During 'Upfront' Window Therapy for All High-Risk Patients

35 mg/m^2/dose (1.2 mg/kg/dose for patients < 10 kg) on Days 1 and 8 of Cycles 1 and 2.

##### On Day 1

Administer diphenhydramine (1 mg/kg, max 50 mg) immediately upon completion of irinotecan infusion. Begin temsirolimus infusion 30 minutes after administration of diphenhydramine.

##### On Day 8

Administer diphenhydramine (1 mg/kg, max 50 mg) immediately upon completion of vinCRISTine. Begin temsirolimus infusion 30 minutes after administration of diphenhydramine.

During Post 'Upfront' Window Therapy for All High-Risk **Responder** Patients

35 mg/m^2/dose (1.2 mg/kg/dose for patients < 10 kg) on Days 1 and 8 of Cycles 7 and 10.

##### On Day 1

Administer diphenhydramine (1 mg/kg, max 50 mg) immediately upon completion of irinotecan infusion. Begin temsirolimus infusion 30 minutes after administration of diphenhydramine.

##### On Day 8

Administer diphenhydramine (1 mg/kg, max 50 mg) immediately upon completion of vinCRISTine. Begin temsirolimus infusion 30 minutes after administration of diphenhydramine.

#### 4.6.5 CISplatin: IV over 6 hours

Recommended hydration and administration guidelines:

Urine specific gravity should be < 1.010 prior to starting CISplatin.

Hours -2 to 0: Prehydrate with 300 mL/m^2 D5 ½ NS + Magnesium sulfate 8 mEq/L + KCL 20 mEq/L.

Hours 0-6: Infuse CISplatin + mannitol 8000 mg/m^2 in 750 mL/m^2 NS @ 125 mL/m^2/hr.

Hours 6- 24: D5½NS+ Magnesium sulfate 8 mEq/L + KCL 20 mEq/L to run at 125 mL/m^2/hr.

During Post 'Upfront' Window Therapy for All High-Risk **Responder** Patients

100 mg/m^2/dose (3.3 mg/kg/dose for patients < 10 kg) on Day 1 of Cycles 3-6 and 8-9.

During Post 'Upfront' Window Therapy for All High-Risk **Non-responder** Patients

100 mg/m^2/dose (3.3 mg/kg/dose for patients < 10 kg) on Day 1 of Cycles 3-8.

#### 4.6.6 5-Fluorouracil: Slow IV Push over 2-4 minutes

During Post 'Upfront' Window Therapy for All High-Risk **Responder** Patients

600 mg/m^2/dose (20 mg/kg/dose for patients < 10 kg) on Day 2 of Cycles 3-6 and 8-9. .

During Post 'Upfront' Window Therapy For All High-Risk **Non-responder** Patients

600 mg/m^2/dose (20 mg/kg/dose for patients < 10 kg) on Day 2 of Cycles 3-8.

- 4.6.7 Dexrazoxane: Slow IV Push over 5-15 minutes immediately prior to doxorubicin dose  
The elapsed time from the beginning of the dexrazoxane dose to the end of the DOXOrubicin infusion should be 30 minutes or less.

Note: Dexrazoxane administration is not required for patients enrolled in Japan.

During Post 'Upfront' Window Therapy for All High-Risk **Responder** Patients

300 mg/m^2/dose (10 mg/kg/dose for patients < 10 kg) on Days 1 and 2 beginning 15 minutes prior to DOXOrubicin dose in **Cycles 8-9 ONLY**.

During Post 'Upfront' Window Therapy For All High-Risk **Non-responder** Patients

300 mg/m^2/dose (10 mg/kg/dose for patients < 10 kg) on Days 1 and 2 beginning 15 minutes prior to DOXOrubicin dose of **Cycles 7-8 ONLY**

- 4.6.8 DOXOrubicin: IV over 15 minutes

During Post 'Upfront' Window Therapy for All High-Risk **Responder** Patients

30 mg/m^2/dose (1 mg/kg/dose for patients < 10 kg) on Days 1 and 2 of Cycles 3- 6 and 8-9.

During Post 'Upfront' Window Therapy For all High-Risk **Non-responder** Patients

30 mg/m^2/dose (1 mg/kg/dose for patients < 10 kg) on Days 1 and 2 of Cycles 3-8.

Medication errors have occurred due to confusion between DAUNOrubicin and DOXOrubicin. DOXOrubicin is available in a liposomal formulation. Use conventional DOXOrubicin only; the conventional and liposomal formulations are NOT interchangeable.

See [Section 5.0](#) for Dose Modifications based on Toxicities.

The therapy delivery maps (TDMs) for Regimen H are on the next 8 pages (see Sections [4.6.9-4.6.11.b](#))


4.6.9 Regimen H – All High-Risk Patients (Stratum 4) ('Upfront' Window Therapy) Cycles 1 & 2                  All High-Risk patients receive 2 cycles of “upfront” VIT window therapy, with subsequent treatment dependent upon response to “upfront” cycles. This therapy delivery map relates to the first 2 cycles of VIT therapy (Cycles 1& 2). Each cycle lasts 21 days. One cycle is described on this TDM. This TDM is on 1 page. Tumor tissue is strongly encouraged for banking: see ABTR01B1 or other appropriate study for details. Use a copy of this page once for each cycle (please note cycle number below).
	
_____
 
Patient name or initials
 
_____
 
DOB

---	--

Criteria to start Cycle 1 see Section 4.6.1.1. Criteria to start Cycle 2 see Section [4.6.1.2](#)

DRUG	ROUTE	DOSAGE	DAY S	IMPORTANT NOTES	OBSERVATIONS
VinCRISTine (VCR)	IV push over 1 minute**	1.5 mg/m  /dose OR (0.05 mg/kg/dose for < 10 kg)	1 and 8	Maximum dose: 2 mg **or infusion via minibag as per institutional policy	a. History, physical, ht/wt, BSA, VS b. CBC (diff/plt) ( Weekly ) c. Electrolytes, Ca ++ , Mg ++ , PO 4 , creatinine, ALT/AST, bilirubin, total protein/albumin, AFP ^ , triglycerides & cholesterol ^ d. Bilirubin e. Urine glucose ^ f. Tumor disease evaluation ( End of Cycle 2 only ) ^ g. Liver transplant consult should be obtained ASAP post diagnosis but no later than end of Cycle #4. h. POST-TEXT grouping ( End of Cycle 2 only ) ^ ^ See Section 7.5 for details OBTAIN OTHER STUDIES AS REQUIRED FOR GOOD PATIENT CARE
Irinotecan (IRIN)	IV over 90 minutes	50 mg/m  /dose OR (1.67 mg/kg/dose for < 10 kg)	1-5	Maximum dose: 100 mg	
Temsirolimus (TORI)	IV over 30 minutes	35 mg/m  /dose OR (1.2 mg/kg/dose for < 10 kg )	1 and 8	See Section 4.6.4 for diphenhydramine premedication administration details	

Circle Cycle #: **1 (Weeks 1-3) 2 (Weeks 4-6)**      Ht \_\_\_\_\_ cm      Wt \_\_\_\_\_ kg      BSA \_\_\_\_\_ m^2

Date Due	Date Given	Day	VCR mg	IRIN mg	TORI mg	Studies	Comments (Include any held doses, or dose modifications)
			Enter calculated dose above and actual dose administered below				
		1	mg	mg	mg	a, b, c*, d, e	
		2		mg			
		3		mg			
		4		mg			
		5		mg			
		8	mg		mg	b, d, e	
		15				b, e	
		21	Start post window therapy at the end of Cycle 2. Responders will receive 6 cycles of C5VD with 2 cycles of VIT (see Sections 4.6.10.a-4.6.10.d ). Non-responders will receive 6 cycles of C5VD and no further VIT (see Section 4.6.11.a and 4.6.11.b ).			f, g, h	

\* The AFP obtained post Cycle 2/prior to Cycle 3 must be submitted for central review assessment of response in Reporting Period 1. For details see Section 10.3.

See [Section 5.0](#) for Dose Modifications for Toxicities and for general Supportive Care Guidelines see [https://members.childrensoncologygroup.org/prot/reference\\_materials.asp](https://members.childrensoncologygroup.org/prot/reference_materials.asp) under Standard Sections for Protocols

**4.6.10.a Regimen H – Continuation for High-Risk Patients(Stratum 4): Window Therapy for Responders Cycles 3, 4, 5 and 6 (C5VD)**

Responders to “upfront” VIT window therapy will next receive C5VD and VIT chemotherapy: a total of 6 cycles of C5VD and 2 more cycles of VIT. This therapy delivery map relates to 4 cycles of C5VD therapy (Cycles 3-6). Each cycle lasts 21 days. One cycle is described on this TDM. This TDM is on 1 page. Use a copy of this page once for each cycle (please note cycle number below).  
Tumor resection or liver transplant should occur whenever feasible BUT ideally by the end of Cycle 6 (4th C5VD cycle) and prior to any further VIT. Patients should resume chemotherapy as soon as possible following surgical resection and within 42 days of surgery or will be off protocol therapy.

\_\_\_\_\_  
Patient name or initials

\_\_\_\_\_  
DOB

Criteria to start each cycle: see [Section 4.6.1.2](#)

DRUG	ROUTE	DOSAGE	DAYS	IMPORTANT NOTES	OBSERVATIONS
CISplatin (CDDP)	IV over 6 hours	100 mg/m  /dose OR (3.3 mg/kg/dose for < 10 kg)	1	Recommended administration guidelines: Urine S.G. should be < 1.010 prior to starting CDDP. See Section 4.6.5 for pre- and post-hydration & mannitol guidelines.	a. History, physical, ht/wt, BSA, VS b. CBC (diff/plt) ( Weekly ) c. Electrolytes, Ca ++ , Mg ++ , PO 4 , creatinine, ALT/AST, bilirubin, total protein/albumin, AFP ^ , triglycerides & cholesterol ^ , urine glucose ^ d. Tumor disease evaluation ( End of Cycles 4 and 6 only ) ^ e. Liver transplant consult should be performed ASAP post diagnosis but no later than FIRST day of Cycle 5. f. Consent for PLUTO registry should be obtained within one month of liver transplant, see (See Section 13.4 ) g. See Section 14.0 for details regarding pathology slides/tumor tissue. h. POST-TEXT grouping (when scans are performed - End of Cycles 4 and 6 if appropriate ) ^ i. Audiogram ( End of Cycle 6 only ) j. Echocardiogram or MUGA ( End of Cycle 6 only ) ^ See Section 7.5 for details OBTAIN OTHER STUDIES AS REQUIRED FOR GOOD PATIENT CARE
5-Fluorouracil (FU)	Slow IV push over 2-4 minutes	600 mg/m  /dose OR (20 mg/kg/dose for < 10 kg)	2		
VinCRISine (VCR)	IV push over 1 minute**	1.5 mg/m  /dose OR (0.05 mg/kg/dose for < 10 kg)	2, 9 and 16	Maximum dose: 2 mg **or infusion via minibag as per institutional policy	
DOXOrubicin (DOXO)	IV over 15 minutes	30 mg/m  /dose OR (1 mg/kg/dose for < 10 kg)	1 & 2		

Circle Cycle #:      **3 (Wks 7-9)**   **4 (Wks 10-12)**   **5 (Wks 13-15)**   **6 (Wks 16-18)**   Ht \_\_\_\_\_ cm      Wt \_\_\_\_\_ kg      BSA \_\_\_\_\_ m^2

Date Due	Date Given	Day	CDDP mg	FU mg	VCR mg	DOXO mg	Studies	Comments (Include any held doses, or dose modifications)	
Enter calculated dose above and actual dose administered below									
		1	mg			mg	a, b, c*, e		
		2		mg	mg	mg			
		9			mg		b		
		16			mg		b		
		21	If feasible, proceed to tumor resection or transplant at the end of Cycle 6. See Section 4.6.10.b. to start Cycle 7.					d, f, g, h, i, j	

\* The AFP obtained post Cycle 2/prior to Cycle 3 must be submitted for central review assessment of response in Reporting Period 1. For details see Section 10.3.

Note: If an AFP was obtained post Cycle 2, do not repeat prior to Cycle 3.

See [Section 5.0](#) for Dose Modifications for Toxicities and for general Supportive Care Guidelines see

[https://members.childrensoncologygroup.org/prot/reference\\_materials.asp](https://members.childrensoncologygroup.org/prot/reference_materials.asp) under Standard Sections for Protocols

**4.6.10.b Regimen H – Continuation for High-Risk Patients (Stratum 4): Window Therapy Responders  
Cycle 7 (VIT)**

This therapy delivery map relates to 1 cycle of VIT therapy and will last 21 days. One cycle is described on this TDM. This TDM is on 1 page. Tumor resection or liver transplant should have occurred prior to any additional post Cycle 2 VIT therapy. Patients should resume chemotherapy as soon as possible following surgical resection and within 42 days of surgery or will be off protocol therapy. The order of chemotherapy cycles can be switched at the discretion of the treating oncologists and surgeons to optimize surgical outcomes and minimize complications (see [Section 4.6](#) for details).

\_\_\_\_\_  
Patient name or initials

\_\_\_\_\_  
DOB

Criteria to start each cycle: See [Section 4.6.1.2](#)

DRUG	ROUTE	DOSAGE	DAYS	IMPORTANT NOTES	OBSERVATIONS
VinCRiStine (VCR)	IV push over 1 minute**	1.5 mg/m  /dose OR (0.05 mg/kg/dose for < 10 kg)	1 & 8	Maximum dose: 2 mg **or infusion via minibag as per institutional policy	a. History, physical, ht/wt, BSA, VS b. CBC (diff/plt) ( Weekly ) c. Electrolytes, Ca ++ , Mg ++ , PO 4 , creatinine, ALT/AST, bilirubin, total protein/albumin, AFP, triglycerides & cholesterol ^ , urine glucose ^ d. Bilirubin  ^ See Section 7.5 for details OBTAIN OTHER STUDIES AS REQUIRED FOR GOOD PATIENT CARE
Irinotecan (IRIN)	IV over 90 minutes.	50 mg/m  /dose OR (1.67 mg/kg/dose for < 10 kg)	1-5	Maximum dose: 100 mg	
Temsirolimus (TORI)	IV over 30 minutes	35 mg/m  /dose OR (1.2 mg/kg for < 10 kg)	1& 8	See Section 4.6.4 for diphenhydramine premedication administration details	

Enter Cycle #: \_\_\_\_\_ Ht \_\_\_\_\_ cm Wt \_\_\_\_\_ kg BSA \_\_\_\_\_ m^2

Date Due	Date Given	Day	VCR mg	IRIN mg	TORI mg	Studies	Comments (Include any held doses, or dose modifications)	
Enter calculated dose above and actual dose administered below								
		1	mg	mg	mg	a, b, c, d		
		2		mg				
		3		mg				
		4		mg				
		5		mg				
		8	mg		mg	b, d		
		15				b		
		21	See Section 4.6.10.c to start Cycle 8.					

See [Section 5.0](#) for Dose Modifications for Toxicities and for general Supportive Care Guidelines see [https://members.childrensoncologygroup.org/prot/reference\\_materials.asp](https://members.childrensoncologygroup.org/prot/reference_materials.asp) under Standard Sections for Protocols.

**4.6.10.c Regimen H – Continuation for High-Risk Patients (Stratum 4): Window Therapy Responders Cycles 8 and 9 (C5VD + DXRZ)**

This therapy delivery map relates to 2 Cycles of C5VD + DXRZ therapy (Cycles 8 and 9). Each Cycle lasts 21 days. One cycle is described on this TDM. This TDM is on 1 page. Patients should resume chemotherapy as soon as possible following surgical resection and within 42 days of surgery or will be off protocol therapy. The order of chemotherapy cycles can be switched at the discretion of the treating oncologists and surgeons to optimize surgical outcomes and minimize complications (see [Section 4.6](#) for details). Use a copy of this page once for each cycle (please note cycle number below).

\_\_\_\_\_  
Patient name or initials

\_\_\_\_\_  
DOB

Criteria to start each cycle: See [Section 4.6.1.2](#)

DRUG	ROUTE	DOSAGE	DAYS	IMPORTANT NOTES	OBSERVATIONS
CISplatin (CDDP)	IV over 6 hours	100 mg/m  /dose OR (3.3 mg/kg/dose for < 10 kg)	1	Recommended administration guidelines: Urine S.G. should be <1.010 prior to starting CDDP. See Section 4.6.5 for pre- and post-hydration & mannitol guidelines.	a. History, physical, ht/wt, BSA, VS b. CBC (diff/plt) c. Electrolytes, Ca ++ , Mg ++ , PO 4 creatinine, ALT/AST, bilirubin, total protein/albumin, AFP, triglycerides & cholesterol ^ , urine glucose ^  ^ See Section 7.5 for details OBTAIN OTHER STUDIES AS REQUIRED FOR GOOD PATIENT CARE
5-Fluorouracil (FU)	Slow IV push over 2-4 minutes	600 mg/m  /dose OR (20 mg/kg/dose for < 10 kg)	2		
VinCRISTine (VCR)	IV push over 1 minute**	1.5 mg/m  /dose OR (0.05 mg/kg/dose for < 10 kg)	2, 9 and 16	Maximum dose: 2 mg **or infusion via minibag as per institutional policy	
Dexrazoxane  (DXRZ)	Slow IV push over 5-15 minutes # #	300 mg/m  /dose OR (10 mg/kg/dose for < 10 kg)	1 & 2	Give immediately prior to DOXO . The elapsed time from the beginning of the DXRZ to the end of the DOXO infusion should be 30 minutes or less.	
DOXOrubicin (DOXO)	IV over 15 minutes	30 mg/m  /dose OR (1 mg/kg/dose for < 10 kg)	1 & 2		

Enter Cycle #: \_\_\_\_\_ Ht \_\_\_\_\_ cm Wt \_\_\_\_\_ kg BSA \_\_\_\_\_ m^2

Date Due	Date Given	Day	CDDP mg	FU mg	VCR mg	DXRZ  mg	DOXO mg	Studies	Comments (Include any held doses, or dose modifications)	
Enter calculated dose above and actual dose administered below										
		1	mg			mg	mg	a, b, c		
		2		mg	mg	mg	mg			
		9			mg			b		
		16			mg			b		
		21	See Section 4.6.10.d to start Cycle 10.							

Dexrazoxane administration is not required for patients enrolled in Japan.

See [Section 5.0](#) for Dose Modifications for Toxicities and for general Supportive Care Guidelines see [https://members.childrensoncologygroup.org/prot/reference\\_materials.asp](https://members.childrensoncologygroup.org/prot/reference_materials.asp) under Standard Sections for Protocols

**4.6.10.d Regimen H – Continuation for High-Risk Patients (Stratum 4): Window Therapy Responders  
Cycle 10 (VIT)**

This therapy delivery map relates to 1 Cycle of VIT therapy and will last 21 days. One cycle is described on this TDM. This TDM is on 1 page. Tumor resection or liver transplant should have occurred prior to any additional post Cycle 2 VIT therapy. Patients should resume chemotherapy as soon as possible following surgical resection and within 42 days of surgery or will be off protocol therapy. The order of chemotherapy cycles can be switched at the discretion of the treating oncologists and surgeons to optimize surgical outcomes and minimize complications (see [Section 4.6](#) for details).

\_\_\_\_\_  
Patient name or initials

\_\_\_\_\_  
DOB

Criteria to start each cycle: See [Section 4.6.1.2](#)

DRUG	ROUTE	DOSAGE	DAYS	IMPORTANT NOTES	OBSERVATIONS
VinCRiStine (VCR)	IV push over 1 minute**	1.5 mg/m  /dose OR (0.05 mg/kg/dose for < 10 kg)	1 & 8	Maximum dose: 2 mg **or infusion via minibag as per institutional policy	a. History, physical, ht/wt, BSA, VS b. CBC (diff/plt) ( Weekly ) c. Electrolytes, Ca ++ , Mg ++ , PO 4 , creatinine, ALT/AST, total protein/albumin, AFP, triglycerides & cholesterol ^ , urine glucose ^ d. Bilirubin e. Tumor disease evaluations f. Echocardiogram or MUGA g. Audiogram  ^ See Section 7.5 for details OBTAIN OTHER STUDIES AS REQUIRED FOR GOOD PATIENT CARE
Irinotecan (IRIN)	IV over 90 minutes.	50 mg/m  /dose OR (1.67 mg/kg/dose for < 10 kg)	1-5	Maximum dose: 100 mg	
Temsirolimus (TORI)	IV over 30 minutes	35 mg/m  /dose OR (1.2 mg/kg for < 10 kg)	1& 8	See Section 4.6.4 for diphenhydramine premedication administration details	

Cycle #: 10 (Wks 28-30)      Ht \_\_\_\_\_ cm      Wt \_\_\_\_\_ kg      BSA \_\_\_\_\_ m^2

Date Due	Date Given	Day	VCR mg	IRIN mg	TORI mg	Studies	Comments (Include any held doses, or dose modifications)
Enter calculated dose above and actual dose administered below							
		1	mg	mg	mg	a, b, c, d	
		2		mg			
		3		mg			
		4		mg			
		5		mg			
		8	mg		mg	b, d	
		15				b	
		21	Completion of Cycle 10 is the end of therapy for High-Risk (Stratum 4) Responders			a, b, c, e, f, g	

See [Section 5.0](#) for Dose Modifications for Toxicities and for general Supportive Care Guidelines see [https://members.childrensoncologygroup.org/prot/reference\\_materials.asp](https://members.childrensoncologygroup.org/prot/reference_materials.asp) under Standard Sections for Protocols.

**4.6.11.a Regimen H – High-Risk Patients (Stratum 4): Window Therapy Non-responders Cycles 3-6 (C5VD)**

This therapy delivery map relates to 4 Cycles of C5VD therapy (Cycles 3-6). Each Cycle lasts 21 days. One cycle is described on this TDM. This TDM is on 1 page. Use a copy of this page once for each cycle (please note cycle number below.)  
Tumor resection or liver transplant should occur whenever feasible BUT ideally by the end of Cycle 6 (4th C5VD cycle). Patients should resume chemotherapy as soon as possible and within 42 days of surgery or will be off protocol therapy.

\_\_\_\_\_  
Patient name or initials

\_\_\_\_\_  
DOB

Criteria to start each cycle: ANC ≥ 750/μL and the platelet count is ≥ 75,000/μL.

DRUG	ROUTE	DOSAGE	DAYS	IMPORTANT NOTES	OBSERVATIONS
CISplatin (CDDP)	IV over 6 hours	100 mg/m  /dose OR (3.3 mg/kg/dose for < 10 kg)	1	Recommended administration guidelines: Urine S.G. should be < 1.010 prior to starting CDDP. See Section 4.6.5 for pre- and post- hydration & mannitol guidelines.	a. History, physical, ht/wt, BSA, VS b. CBC (diff/plt) ( Weekly ) c. Electrolytes, Ca ++ , Mg ++ , PO 4 , creatinine, ALT/AST, bilirubin, total protein/albumin, AFP ^ , triglycerides & cholesterol ^ , urine glucose ^ d. Tumor disease evaluation ( End of Cycles 4 & 6, Only ) ^ e. Audiogram ( End of Cycle 6 only ) f. Echocardiogram or MUGA ( End of Cycle 6 only ) g. Liver transplant consult should be performed ASAP post diagnosis but no later than FIRST day of Cycle 5. h. Consent for PLUTO registry should be obtained within one month of liver transplant, see Section 13.4 i. POST-TEXT grouping (when scans are performed - End of Cycle 4 & 6 if appropriate ) ^ j. See Section 14.0 for details regarding pathology slides/tumor tissue. ^ See Section 7.5 for details OBTAIN OTHER STUDIES AS REQUIRED FOR GOOD PATIENT CARE
5-Fluorouracil (FU)	Slow IV push over 2-4 minutes	600 mg/m  /dose OR (20 mg/kg/dose for < 10 kg)	2		
VinCRISTine (VCR)	IV push over 1 minute**	1.5 mg/m  /dose OR (0.05 mg/kg/dose for < 10 kg)	2, 9 and 16	Maximum dose: 2 mg **or infusion via minibag as per institutional policy	
DOXOrubicin (DOXO)	IV over 15 minutes	30 mg/m  /dose OR (1 mg/kg/dose for < 10 kg)	1 & 2		

Circle Cycle #:    3 (Wks 7-9)    4 (Wks 10-12)    5 (Wks 13-15)    6 (Wks 16-18)    Ht \_\_\_\_\_ cm    Wt \_\_\_\_\_ kg    BSA \_\_\_\_\_ m^2

Date Due	Date Given	Day	CDDP mg	FU mg	VCR mg	DOXO mg	Studies	Comments (Include any held doses, or dose modifications)	
Enter calculated dose above and actual dose administered below									
		1	_____ mg			_____ mg	a, b, c*, h		
		2		_____ mg	_____ mg	_____ mg			
		9			_____ mg		b		
		16			_____ mg		b		
		21	If feasible, proceed to tumor resection or transplant at the end of Cycle 6. See Section 4.6.10.b. to start Cycle 7.					d, e, h, i, j	

\* The AFP obtained post Cycle 2/prior to Cycle 3 must be submitted for central review assessment of response in Reporting Period 1. For details see Section 10.3.  
Note: If an AFP was obtained post Cycle 2, do not repeat prior to Cycle 3.

See [Section 5.0](#) for Dose Modifications for Toxicities and for general Supportive Care Guidelines see [https://members.childrensoncologygroup.org/prot/reference\\_materials.asp](https://members.childrensoncologygroup.org/prot/reference_materials.asp) under Standard Sections for Protocols.

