### Regimen H for Non-Responders

Cycle	1	2	Eval	3	4	5	6	7	8
Week	1	4			7	10	13	16	19
Chemotherapy	VIT	VIT		C5VD	C5VD	C5VD	C5VD	C5VD+ DXRZ*	C5VD+ DXRZ*

Non responders will receive 6 total cycles of C5VD post VIT window.

\*Dexrazoxane administration is not required for patients enrolled in Japan.

**NOTE: For high-risk patients being assessed at the end of Cycle 2, the central review assessment will be returned to the institutional investigator and will indicate the post-induction treatment regimen.**

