#### 4.6.1 Criteria to Start Cycle 1 of Regimen H and Subsequent Cycles

##### 4.6.1.1 Criteria to Start Cycle 1 of Regimen H for All High-Risk Patients

Begin Cycle 1 of Regimen H, when ANC  $\geq$  750/ $\mu$ L and the platelet count is  $\geq$  75,000/ $\mu$ L and all the eligibility criteria have been met.

4.6.1.2 Criteria to Start Cycle 2 of Regimen H for **All High-Risk Patients** and Cycles 3-10 of Regimen H for All High-Risk **Responders**

- ANC  $\geq 750/\mu\text{L}$  and the platelet count is  $\geq 75,000/\mu\text{L}$ .
- Total Cholesterol  $\leq 400$  mg/dL OR  $\leq 500$  mg/dL and on lipid lowering medication, AND triglycerides  $\leq 300$  mg/dL OR  $\leq 500$  mg/dL and on lipid lowering medication. If cholesterol or triglyceride parameters are not met based on testing performed in a non-fasting patient, these tests should be repeated after fasting.

4.6.1.3 Criteria to Start Cycles 3-8 of Regimen H for All High-Risk **Non-Responder** Patients

- ANC  $\geq 750/\mu\text{L}$  and the platelet count is  $\geq 75,000/\mu\text{L}$ .

Note: Beyond Cycle 2, the cholesterol and triglyceride parameters to start a cycle of therapy are not applicable for non-responders, as they will not receive any further VIT therapy.

Note: All patients  $< 10$  kg will have dosing in mg/kg

4.6.2 VinCRiStine: IV Push over 1 minute or infusion via minibag as per institutional policy During 'Upfront' Window Therapy for All High-Risk Patients

1.5 mg/m^2/dose (0.05 mg/kg/dose for patients  $< 10$  kg) [Maximum dose: 2 mg] on Days 1 and 8 of Cycles 1 and 2.

During Post 'Upfront' Window Therapy for All High-Risk Responder Patients

1.5 mg/m^2/dose (0.05 mg/kg/dose for patients  $< 10$  kg) [Maximum dose: 2 mg] on Days 2, 9 and 16 of Cycles 3-6, 8-9 **and** Days 1 and 8 of Cycles 7 and 10.

During Post 'Upfront' Window Therapy for All High-Risk Non-responder Patients

1.5 mg/m^2/dose (0.05 mg/kg/dose for patients  $< 10$  kg) [Maximum dose: 2 mg] on Days 2, 9 and 16 of Cycles 3-8.

Special precautions: FOR INTRAVENOUS USE ONLY.

The container or the syringe containing vinCRiStine must be enclosed in an overwrap bearing the statement "Do not remove covering until moment of injection. For intravenous use only - Fatal if given by other routes."

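### Minor: the non-responder delivery map in Section 4.6.11.a sends sites to the responders' VIT page for Cycle 7, and its Studies column leaves out the echocardiogram/MUGA and the transplant consult

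*Combined protocol and SAP*

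**What the plan says.** Section 4.6.11.a is the dosing and recording page headed "Window Therapy Non-responders Cycles 3-6 (C5VD". Its Day 21 row reads "If feasible, proceed to tumor resection or transplant at the end of Cycle 6. See Section 4.6.10.b. to start Cycle 7". The page it names, Section 4.6.10.b, is headed "Continuation for High-Risk Patients (Stratum 4): Window Therapy Responders" and sets out one 21-day cycle of VIT.

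Elsewhere the plan for non-responders is consistent. The regimen table in Section 4.6 says "Non responders will receive 6 total cycles of C5VD post VIT window". Section 4.6.1.3 drops the lipid criteria for non-responders after Cycle 2 "as they will not receive any further VIT therapy". Sections 4.6.7 and 4.6.8 place their dexrazoxane in Cycles 7-8 and their doxorubicin in Cycles 3-8. The window map, Section 4.6.9, names 4.6.11.a and 4.6.11.b as the non-responder pages.

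Map 4.6.11.a also lists ten observations, a to j. Item f is the echocardiogram or MUGA at the end of Cycle 6. Item g is the consult: "Liver transplant consult should be performed ASAP post diagnosis but no later than FIRST day of Cycle 5". The Studies column prints `a, b, c*, h` on Day 1, `b` on Days 9 and 16, and `d, e, h, i, j` on Day 21.

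**The concern.** Sites use the delivery maps to schedule treatment and to record the doses given, so an error here sits on an operative page. Followed literally, the Day 21 pointer takes a child whose tumor did not respond to VIT to another cycle of VIT in place of the planned C5VD.

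The missing f removes the day-row prompt for a cardiac check made just before the last two doxorubicin cycles. Section 5.2.2 uses that kind of result, an ejection fraction below 47% or a shortening fraction below 27%, to decide whether doxorubicin is omitted. The missing g removes a prompt for the transplant consult. What is at stake is patient safety and fidelity of treatment, not inference.

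**Working it through.** The main check is a side-by-side reading, with a little arithmetic for scale.

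**Step 1: the pointer.**

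| Place | Non-responder treatment in Cycle 7 |
|---|---|
| Section 4.6, text and non-responder table | C5VD with dexrazoxane; VIT stops after Cycle 2 |
| Section 4.6.1.3 | C5VD; lipid criteria not applied because VIT has ended |
| Sections 4.6.7-4.6.8 | doxorubicin, with dexrazoxane (not required in Japan) |
| Map 4.6.9, Day 21 row | C5VD only; continue on 4.6.11.a and 4.6.11.b |
| Map 4.6.11.a, Day 21 row | go to 4.6.10.b, which is VIT |

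Only the last row disagrees. The same sentence stands on the responder map, Section 4.6.10.a, where it is right, so it was probably carried over without being updated. The correct target is Section 4.6.11.b.

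**Step 2: the letters.** The responder map carries the same ten items in a different order. Translating its day rows item by item gives:

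| Item | Letter and day on 4.6.10.a | Letter on 4.6.11.a | Day printed on 4.6.11.a |
|---|---|---|---|
| History and physical | a, Day 1 | a | Day 1 |
| CBC | b, Days 1, 9, 16 | b | Days 1, 9, 16 |
| Chemistry, AFP, lipids | c*, Day 1 | c* | Day 1 |
| Tumor evaluation | d, Day 21 | d | Day 21 |
| Transplant consult | e, Day 1 | g | none |
| PLUTO consent | f, Day 21 | h | Day 1 and Day 21 |
| Pathology | g, Day 21 | j | Day 21 |
| POST-TEXT grouping | h, Day 21 | i | Day 21 |
| Audiogram | i, Day 21 | e | Day 21 |
| Echocardiogram or MUGA | j, Day 21 | f | none |

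The responder map schedules all ten of its letters. The non-responder map schedules eight: f and g are absent and h appears twice. By this translation the rows would be `a, b, c*, g` on Day 1 and `d, e, f, h, i, j` on Day 21.

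**Step 3: where the missing cardiac check falls.** Doxorubicin is 30 mg/m2 on two days per C5VD cycle.
- Through Cycle 6 (four C5VD cycles): 4 × 2 × 30 = 240 mg/m2.
- Remaining, Cycles 7-8: 2 × 2 × 30 = 120 mg/m2.
- Total: 240 + 120 = 360 mg/m2, matching the study's entry in Table 3.

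Section 7.5 schedules the echocardiogram or MUGA at baseline, at the end of Cycle 6 and at end of therapy. The missing letter is therefore the only scheduled check in between.

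**Step 4: what the linked page would deliver.** One VIT cycle at full dose, subject to the per-dose caps:
- irinotecan 5 × 50 = 250 mg/m2;
- temsirolimus 2 × 35 = 70 mg/m2;
- vincristine 2 × 1.5 = 3 mg/m2.

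**The case against.** The strongest reply is that several safeguards stand between these slips and a patient.

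- Sections 4.6 and 7.5, the governing text, are correct.
- Central review after Cycle 2 tells the site which post-induction regimen applies. Under Sections 4.6 and 8.1(l), choosing another takes the patient off protocol therapy.
- The linked page is visibly headed for responders, and its start criteria refer to Section 4.6.1.2, whose criteria for Cycles 3-10 are for responders.
- Items f and g are printed with their timing in the map's own Observations list.
- The consult is already prompted for every high-risk patient on map 4.6.9: "Liver transplant consult should be obtained ASAP post diagnosis but no later than end of Cycle #4". The g omission therefore adds little.
- The letters come from a table read out of a PDF, and a reading fault cannot be fully excluded.

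All of this stands, and it is why the point is minor. It does not make the pointer right for a non-responder. A reading fault also seems unlikely, because the responder map came through with all its letters.

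A reader might infer more than the documents support:

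- **That non-responders received VIT, or missed a cardiac check.** Nothing in the documents shows this.
- **That every window non-responder was exposed to the wrong pointer.** It acts only at Day 21 of Cycle 6. Patients who progress, refuse, or leave protocol therapy for other reasons never reach it, and no attrition rate is given, so no count of exposed patients can be derived.
- **That page 4.6.11.b is missing from the plan.** It is not in the text available here, but Sections 4.6.8 and 4.6.9 refer to it. Its absence may reflect only how the text was extracted.
- **That the trial's results are compromised.** The Stratum 4 response endpoint in Section 9.2 is read at the end of Cycle 2, before this page's Day 21 pointer applies. The referral rule in the same section is unchanged by a missing letter.

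**Conclusion.** Wrong as written, and minor. The pointer error is certain from the text: one row of one map contradicts every other statement of non-responder therapy. The absence of f and g from the Studies column is clear in the available text. The corrected Day 1 letter is an inference from the responder map, where the same consult, "e. Liver transplant consult should be performed ASAP post diagnosis but no later than FIRST day of Cycle 5", is scheduled on Day 1; the plan does not state the intended lettering.

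The size is one wrong cross-reference and two missing letters on one page. Of the two, f matters more, because it marks the single mid-treatment cardiac check, with 120 mg/m2 of doxorubicin still to come. The consequence is a limited risk to safety and treatment fidelity. No endpoint, sample size or decision rule is affected.

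**What to change.** On map 4.6.11.a:

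- Day 21 row: change the reference from Section 4.6.10.b to Section 4.6.11.b, and add f, so that the Studies entry reads `d, e, f, h, i, j`.
- Day 1 row: after checking the letters against the original PDF, replace h with g, so that it reads `a, b, c*, g`.

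The cost is an editorial correction to one page, with no change to treatment, analysis or sample size. The study is marked closed on July 20, 2018, so the sponsor may also wish to look through existing records for VIT given to non-responders from Cycle 7 on, and for an echocardiogram or MUGA before Cycle 7 doxorubicin. That check is optional; the correction does not depend on it.
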